4.1. Overall Design

Study I8H-MC-BDCL (BDCL) is a multicenter, randomized, open-label, parallel, comparator-controlled Phase 2 study with 3 study periods. The study is designed to evaluate the efficacy and safety of LY3209590 compared with insulin degludec in patients with T2DM treated with a stable dose of metformin (alone or in combination with a stable dose of a DPPIV inhibitor and/or a SGLT2 inhibitor) for at least 3 months prior to screening.

The study will consist of 3 periods:

- Study Period 1: screening and lead-in period, approximately 2 weeks
- Study Period 2: treatment period, 26 weeks
- Study Period 3: safety follow-up period, 5 weeks

The study schema is presented in Section 1.2.

Study governance considerations are described in detail in Section 10.1.

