Study Period 3: End-of-Treatment and Safety Follow-up, Visits 20, 801, Early Discontinuation 1 and 2 (ED1 and ED2)

All randomized participants should have a comprehensive efficacy and safety evaluation at Visit 20 and a safety follow-up visit approximately 6 weeks after the last dose of LY3209590 and 5 weeks after the last dose of insulin degludec. During the safety follow-up study period, participants will continue SMBG and may be treated with an appropriate glucose-lowering regimen (see table in Section 6.5) if appropriate. Participants will also be required to return the study diary and used or unused IP to the investigative site.

Participants who *complete the treatment period* will have a comprehensive End-of-Treatment efficacy and safety assessment (Week 26; Visit 20). The safety follow-up assessment (Visit 801) should occur approximately 5 weeks after their End-of-Treatment assessment (Visit 20). Participants will also be required to return used and unused IP as well as the study diary to the investigative site at V801.

Participants who *discontinue IP prior to completion* of the treatment period for any reason should also have a comprehensive End-of-Treatment efficacy and safety assessment (early discontinuation [ED]1) approximately 1 week after the last dose of LY3209590 or as soon as reasonably possible thereafter, and should have a safety follow-up assessment (ED2)

approximately 5 weeks after ED1. Study activities at Visits ED1 and ED2 are identical to Week 26 (Visit 20) and Visit 801, respectively. CCI

and the switch to an alternative, commercially available insulin must be closely monitored to prevent hypoglycemia due to an accumulation of insulin action.

Participants who discontinue IP prior to the completion of the treatment period will be encouraged to remain in the study and to complete any scheduled study procedures until Visit 20. Participants remaining in the study will receive an appropriate glucose-lowering regimen. Table in Section 6.5 provides details on the use of glucose-lowering medications, which can be used.

Participants who *discontinue IP for any reason and are unwilling to return for a safety follow-up* visit, will be asked to perform an early termination (ET) visit as their final study visit. At this visit, participants will perform procedures listed in the Schedule of Activities (Section 1.3).

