8.3.7.1. Hypoglycemia

Patients will collect information on episodes of hypoglycemia starting from Visit 2 until the last study visit (Visit 801 or ET visit). For that purpose, patients will be trained about signs and symptoms of hypoglycemia, how to treat hypoglycemia, and how to collect in study diaries appropriate information for each episode of hypoglycemia according to the Schedule of Activities (Section 1.3).

Participants are encouraged to perform SMBG, whenever hypoglycemia may be suspected, either by symptoms experienced or perceived increased risk as related to dietary intake, physical activity, or inadvertent or atypical insulin dosing. All patients will be instructed to treat a SMBG ≤ 70 mg/dL (< 3.9 mmol/L) as hypoglycemia.

Participants will be instructed to report hypoglycemia in the eDiary any time he/she experiences signs or symptoms of hypoglycemia with or without a SMBG ≤ 70 mg/dL (< 3.9 mmol/L).

Severe hypoglycemia is defined as an event requiring assistance of another person to actively administer carbohydrate, glucagon, or other resuscitative actions. During these episodes, the participant has an altered mental status and cannot assist in his/her own care, may be semiconscious or unconscious, or experience coma with or without seizures, and may require parenteral therapy. Glucose measurements may not be available during such an event, but neurological recovery attributable to the restoration of blood glucose concentration to normal is considered sufficient evidence that the event was induced by a low blood glucose concentration (≤ 70 mg/dL [< 3.9 mmol/L]).

If a hypoglycemic event meets the criteria of severe as confirmed by the investigator, it needs to be recorded as serious on the AE eCRF and reported to Lilly as a SAE.

In each case of suspected or confirmed hypoglycemia, it is important that the event be properly categorized, the effect of the intervention be assessed, and the frequency and duration of hypoglycemia be evaluated. The role of dietary changes and physical exercise (or any other contributing factor) in the development of an event should be established. The patient should receive additional education, if deemed appropriate. Management of increased risk of hypoglycemia is described in Section 6.1.2.2.

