Incidence of hypoglycemia events for Level 1 and Level 2/3 
 • Documented • Nocturnal • Non-Nocturnal 	0-12, 0-26, 12-26 weeks, post-treatment period (up to Visit 801)*	Logistic regression will include treatment, baseline HbA1c in the model. Note that the logistic regression will be conducted when ≥ 10 patients with this event.

 • Proportion of patients with HbA1c <7% without documented nocturnal hypoglycemia event (Level 1 and Level 2) • Proportion of patients with HbA1c $\leq 6.5\%$ without documented nocturnal hypoglycemia event (Level 1 and Level 2) 	0-26 weeks	Logistic regression will include treatment, country, DPPIV [yes/no], SGLT2 [yes/no], baseline BMI [<30 , ≥ 30], and baseline HbA1c in the model.

Abbreviations: BMI = body mass index; HbA1c = hemoglobin A1c; Level 2/3= Level 2 and Level 3 composite.
Note: The hypoglycemia rate per year during defined period is calculated by the number of hypoglycemia within the period/number of days patient at risk within the period*365.25 days. The hypoglycemia incidence during defined period indicates if the patient has at least 1 hypoglycemia events within the period (Yes/No). The baseline hypoglycemia rate is the rate calculated between Visit 2 and Visit 3.

*Analyses for endpoint during post-treatment period (up to Visit 801) will include all of the data after study drug discontinued on Safety population; analyses for endpoints during other time points will include all data before study drug discontinued on Safety population.

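### The post-treatment hypoglycemia window has no limit on time since end of treatment, so completers with about 5 weeks at risk are pooled with early discontinuers who may have many more, and the incidence model ignores the difference

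*SAP*

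**What the plan says.** The exploratory objectives (protocol section 3, SAP 4.3) include the incidence and rate of hypoglycemia in follow-up after treatment. Protocol 9.4.6.3 lists the follow-up period as one of the analysis periods, and the protocol's design section gives its length: "Study Period 3: safety follow-up period, 5 weeks".

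The SAP sets the data rule in the footnote to Table BDCL.1 (5.10.3.2): "Analyses for endpoint during post-treatment period (up to Visit 801) will include all of the data after study drug discontinued on Safety population". Two analyses use it, and both compare the arms:

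- **Rate.** Defined as "number of hypoglycemia within the period/number of days patient at risk within the period*365.25 days", and compared by the empirical method of SAP Appendix 1.
- **Incidence.** "The hypoglycemia incidence during defined period indicates if the patient has at least 1 hypoglycemia events within the period (Yes/No"). For the model, "Logistic regression will include treatment, baseline HbA1c in the model".

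The protocol keeps early discontinuers under observation. Section 4.1.1 says "Participants who discontinue IP prior to the completion of the treatment period will be encouraged to remain in the study", up to Visit 20, and "Participants remaining in the study will receive an appropriate glucose-lowering regimen". Section 7.1.1 likewise has those who stop permanently carry on in the trial. Section 8.3.7.1 has hypoglycemia recorded "until the last study visit (Visit 801 or ET visit"). Footnote c to the Schedule of Activities gives Visit 801 to those who complete Visit 20, and ED1 and ED2 (5 weeks after ED1) to those who stop drug but remain in the study.

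**The concern.** The window is set by a calendar visit, not by time since treatment ended. Its length is therefore about 5 weeks for a completer, but for an early discontinuer it depends on when drug was stopped and how long the participant stayed.

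For incidence, a longer time at risk gives a larger chance of at least one event at the same underlying rate, and the logistic model has no term for time at risk. If the arms differ in how many participants stop and stay, the incidence comparison can differ with no difference in hypoglycemia risk.

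The rate is per day at risk, so unequal duration alone does not bias it in that way. It does average two different things: the weeks soon after stopping, and time months later. For a once-weekly insulin, hypoglycemia soon after stopping is the natural safety question, and a pooled figure answers it less clearly.

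**Working it through.** **Timeline.** The documents state no figure for post-treatment person-time. Their timeline reproduces: 2 + 26 + 5 = 33 weeks maximum participation, and 26 + 5 = Week 31 for Visit 801.

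**Time at risk per participant.** Let *w* be the week in which exposure ends. SAP 5.10.1 defines this as the last dose for insulin degludec and the last dose + 7 days for LY3209590.

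- Completer: 31 − 26 = 5 weeks.
- Early discontinuer followed to Visit 801: 31 − *w*. One LY3209590 dose at Week 0 gives *w* = 1, so 30 weeks.
- Followed to Visit 20 only: 26 − *w*.
- Followed to ED2 only: about 5 weeks.

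**Share of person-time.** The documents do not say how many participants stop drug yet stay in the study. Call this proportion *f* and assume 5%, 10% or 20%. Assume *w* is spread evenly over Weeks 1 to 25. The mean of 31 − *w* is then 31 − 13 = 18 weeks, of which 18 − 5 = 13 lie beyond the 5-week window.

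- Discontinuers' share = 18*f* / (18*f* + 5(1 − *f*))
- Share of the total beyond 5 weeks = 13*f* / (18*f* + 5(1 − *f*))

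| *f* | Denominator | Discontinuers' share | Beyond 5 weeks |
|---|---|---|---|
| 5% | 0.90 + 4.75 = 5.65 | 0.90/5.65 = 16% | 0.65/5.65 = 12% |
| 10% | 1.80 + 4.50 = 6.30 | 1.80/6.30 = 29% | 1.30/6.30 = 21% |
| 20% | 3.60 + 4.00 = 7.60 | 3.60/7.60 = 47% | 2.60/7.60 = 34% |

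**Less retention.** If all discontinuers leave at Visit 20, the mean is 26 − 13 = 13 weeks, and the shares 13*f* / (13*f* + 5(1 − *f*)) are 12%, 22% and 39%. If all leave at ED2, the shares are 5%, 10% and 20%, equal to head count, and nothing lies beyond 5 weeks. At *f* = 20% with half retained to Week 31 and half to ED2, per arm of 125: 25 × (0.5 × 18 + 0.5 × 5) = 287.5 of 787.5 person-weeks, about 36.5%.

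**Incidence illustration.** Assume events occur at a constant 1 per year in everyone, in both arms. The chance of at least one event is 1 − exp(−7 × weeks/365.25): 9.1% over 5 weeks, 29.2% over 18 and 43.7% over 30. Give every stop-and-stay participant 18 weeks.

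- Arm with *f* = 5%: 0.95 × 0.0914 + 0.05 × 0.2918 = 10.1%.
- Arm with *f* = 10%: 0.90 × 0.0914 + 0.10 × 0.2918 = 11.1%.
- Arm with *f* = 20%: 0.80 × 0.0914 + 0.20 × 0.2918 = 13.1%.

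The odds ratio is about 1.11 for 10% against 5% and about 1.34 for 20% against 5%, although the event rate is identical. Rates of 0.5 or 2 per year give nearly the same odds ratios (1.11 and 1.34; 1.11 and 1.34 to two decimals). If *f* is equal in the two arms, with the same stop times and retention, the odds ratio is 1. The distortion therefore needs an imbalance.

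**The case against.** The strongest case for the plan is that this is a stated, consistent all-data choice. SAP 5.10.1 measures follow-up from end of treatment to the last study visit, and SAP 5.10 uses safety data both on and after study drug. Protocol 9.4.1 leaves the detail of the hypoglycemia analyses to the SAP. The endpoint is exploratory, the rate is per day at risk, and severe events are also listed individually. All of that stands and limits the stakes. It does not answer the incidence row, where time at risk is unequal and unadjusted.

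A reader might infer more than the documents support:

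- **That the window has no end.** Visit 801 ends it. What is missing is a limit on time since end of treatment.
- **That early discontinuers swamp the analysis at 30 weeks each.** Thirty weeks needs a Week 1 stop; the mean under even stop times is 18. Even with full retention, discontinuers pass half of person-time only when 18*f* > 5(1 − *f*), that is *f* above 5/23 = 21.7%. The plan's 20% is assumed study dropout, and people who leave the study add little post-treatment time.
- **That the rate ratio is diluted by a known amount.** A ratio of 2.0 for 5 weeks and 1.0 afterwards would be reported as 2 − 0.21 = 1.79 at 10% and 2 − 0.34 = 1.66 at 20%. But protocol 6.7.1 says LY3209590 washout may take up to 10 weeks, so a drop to 1.0 at 5 weeks has no basis in the documents.
- **That replacement drugs are peculiar to early discontinuers.** Protocol 4.1.1 and the table in 6.5 also allow glucose-lowering drugs, including insulin, during safety follow-up. What is peculiar to early discontinuers is the length of observation and its distance from the last dose.

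The washout statement also bears on the remedy: a 35-day window closes about 6 weeks after the last LY3209590 dose, before the stated washout may be complete.

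**Conclusion.** The point holds in limited form. The footnote sets no limit on time since end of treatment, so about 5 weeks from completers is pooled with up to about 30 weeks, at the extreme, from early discontinuers who stay. The incidence comparison is the weaker of the two, because it can differ between arms through unequal stop-and-stay proportions alone. The rate comparison is adjusted for exposure but mixes early and late off-drug time.

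The size rests on a proportion the documents do not give. The range of 16% to 47% of person-time, with 12% to 34% of the total beyond 5 weeks, assumes even stop times and full retention to Week 31, and is upper-end for that reason.

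The documents also disagree on whether this time exists. Protocol 7.2 has a participant who needs another effective agent leave the study before it is started, whereas 4.1.1 and 7.1.1 keep those who stop drug in the study on another regimen. These passages must be reconciled.

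The change is worth making because it is cheap, but the endpoint is exploratory and the secondary treatment-period hypoglycemia endpoint is unaffected.

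**What to change.** In the Table BDCL.1 footnote, define one post-treatment window for the between-arm comparison, the same in both arms and for both the incidence and rate rows: from end of exposure as defined in SAP 5.10.1 to the earlier of 35 days later or the last study visit. This matches the follow-up that completers have, so it compares like with like. Report later off-drug events descriptively, by arm and separately for early discontinuers.

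State the reason for 35 days. The cost is that later events leave the comparison although LY3209590 washout may run to 10 weeks, so the descriptive table should show events up to 10 weeks as well as those beyond. No data are discarded and no collection changes. Protocol 7.2 should be reconciled with 4.1.1 and 7.1.1 at the same time, and the number of participants who stop drug but stay in the study should be reported by arm.

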The amendment provides information to reflect termination of the investigational medical device study arm evaluating the individualized accruing data algorithm (Algorithm 2) investigational device in the Phase 2 Study 18H-MC-BDCL (BDCL). Study BDCL will continue to evaluate dosing regimens of investigational medicinal product LY3209590, a long-acting insulin receptor agonist that is being developed as a basal insulin administered once-weekly for treatment of type 2 diabetes mellitus (T2DM). Study BDCL is evaluating individualized LY3209590 dosing strategies in insulin-naïve study participants with T2DM in the paper algorithm (Algorithm 1). Insulin degludec is an unblinded active comparator in this study.

Lilly is terminating the Algorithm 2 study arm due to the extent of data entry errors generated by patients and the impact these errors have on dosing recommendations from the investigational device Algorithm 2. These errors (missing, unchecked, or uncorrected by site verification) provide less than complete data set inputs that are submitted by the investigator into the Algorithm 2 dosing calculation. The limited data set inputs have revealed shortcomings in dosing calculation confounding factors for the limited number of Algorithm 2 dosing recommendations observed from a limited number of sites and participants during the early enrollment phase. In some cases, if the investigator had not applied clinical judgement to override the recommended dose, a serious adverse consequence on patient health and/or safety associated with the investigational device may have resulted.

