Lilly recognized that the planned expansion to include all sites participating in the United States would increase both the number of participants utilizing the investigational device Algorithm 2 and the number of investigators providing oversight of the Algorithm 2 dosing recommendations. Based on the limited experience to date with Algorithm 2, it was unclear whether all potential issues had been identified or unforeseen future issues might impact the ability to complete the trial. It was concluded that study expansion could increase the risk for dosing errors and the possible identification of previously unidentified issues with Algorithm 2. Importantly, the continued use of investigator override could impair our ability to meet the scientific objectives of the study related to Algorithm 2. This amendment reflects taking the preventive action of terminating the Algorithm 2 investigational medical device trial arm of Study BDCL to prevent further potential patient safety issues and delay in the study.

Section # and Name	Description of Change	Brief Rationale
Throughout the document	Removal of language related to Algorithm 2	Alignment of protocol for removal of Algorithm 2
Section 1.1. Synopsis Section 6.1. Study Intervention(s) Administered Section 9.2. Sample Size Determination Section 10.10. Appendix 10: Change to Study Procedures due to the COVID-19 Pandemic or Natural Disasters	Change in number of participants and randomization ratio	Based on the removal of Algorithm 2, the participant number was updated.
Section 1.3. Schedule of Activities	Addition of language for footnote d	Clarification that a triplicate ECG for insulin degludec is only required one time.
	Addition of language for footnote e	Clarification of the collection of 2 PK samples is for LY3209590.
Section 6.1. Study Interventions(s) Administered	Addition of language for participants transitioning from Algorithm 2	Clarification for participants in Algorithm 2 to proceed with study procedures for those treated with LY3209590.
Section 8.4. Treatment of Overdose	Addition of procedural language	Clarification added to contact the sponsor in case of an accidental overdose.
Section 9.3. Populations for Analysis Section 9.4.1. General Considerations 9.4.2.2. Patient Characteristics Section 9.4.6.3. Hypoglycemia Episodes	Change in language related removal of Algorithm 2	Update of statistical analysis after removal of Algorithm 2

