9.3. Populations for Analyses

The following populations are defined:

Population	Description
Entered/Enrolled Population	All participants who sign the ICF
Randomized Population	All participants assigned to treatment, regardless of whether they take any doses of study treatment, or if they took the correct treatment. The participants previously randomized to Algorithm 2 will be pooled with the participants randomized to Algorithm 1 and all of these participants will be analyzed as one treatment group of LY3209590.
Efficacy Population	Participants in randomization population excluding the participants previously randomized to Algorithm 2.
Safety Population	All participants randomly assigned to study treatment and who take at least 1 dose of study treatment. The participants previously randomized to Algorithm 2 will be pooled with the participants randomized to Algorithm 1 and all of these participants will be analyzed as one treatment group of LY3209590.
Pharmacokinetic Population	All randomized participants who received at least 1 dose of LY3209590 and have at least 1 evaluable PK sample.

Abbreviations: ICF = informed consent form; PK = pharmacokinetics.

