9.4. Statistical Analyses

Statistical analysis of this study will be the responsibility of sponsor or its designee.

All tests of treatment effects will be conducted at a 2-sided alpha level of 0.1, unless otherwise stated, and all confidence intervals (CIs) will be given at a 2-sided 90% level.

Any change to the data analysis methods described in the protocol will require an amendment only if it changes a principal feature of the protocol. Any other change to the data analysis methods described in the protocol, and the justification for making the change, will be described in the statistical analysis plan (SAP) and the clinical study report. Additional exploratory analyses of the data will be conducted as deemed appropriate.

The SAP will include a more technical and detailed description of the statistical analyses described in this section. This section is a summary of the planned statistical analyses of the most important endpoints including primary and key secondary endpoints.

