9.4.1. General Considerations

Unless otherwise stated, the efficacy analyses will be conducted on efficacy analyses set (EAS) based on the Efficacy Population using the data up to the study treatment discontinuation (defined as the observed data with collection date before or at the last dose date +10 days). Sensitivity analyses for selected efficacy measures may be conducted on the Randomized Population using the data up to the study treatment discontinuation.

Unless otherwise stated, the safety analyses except for hypoglycemia will be conducted on the safety analyses set based on the Safety Population using all data collected during the study including treatment and follow-up period regardless of the treatment disposition status. The details for analyses on hypoglycemia will be documented in the SAP.

Unless otherwise specified, the baseline value used for the analyses will be the last non-missing value obtained for each participant prior to or on the date of first study IP dose (or randomization visit date if first dose date is missing). The baseline liver enzyme lab measures will be the average of all assessments prior to and at randomization visit.

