9.4.6.3. Hypoglycemia Episodes

The incidence and rate per year of hypoglycemia will be presented for the periods between 0 to 12 weeks and 12 to 26 weeks, 0 to 26 weeks and the follow-up period and analyzed according to the hypoglycemia definitions described in the ADA classification system (ADA 2019). The analyses for hypoglycemia will be performed on Efficacy Population and additionally severe (level 3) hypoglycemia analyses will also be performed for the Safety Population.

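### SAP Table BDCL.1 analyzes hypoglycemia only on the pooled Safety Population, whereas protocol 9.4.6.3 assigns it to the Efficacy Population, and no reason is given

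*SAP*

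**What the plan says.** **Protocol.** Section 9.4.6.3 states: "The analyses for hypoglycemia will be performed on Efficacy Population and additionally severe (level 3) hypoglycemia analyses will also be performed for the Safety Population". Section 9.3 defines the Efficacy Population as "Participants in randomization population excluding the participants previously randomized to Algorithm 2". Section 9.4.1 sets the general rule that "the safety analyses except for hypoglycemia will be conducted on the safety analyses set based on the Safety Population", and adds: "The details for analyses on hypoglycemia will be documented in the SAP". The amendment (d) summary of changes lists 9.4.6.3 among the revised sections and gives the reason as "Update of statistical analysis after removal of Algorithm 2". For analysis changes that need no amendment, Section 9.4 requires that the change and "the justification for making the change, will be described in the statistical analysis plan (SAP) and the clinical study report".

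**SAP.** The footnote to Table BDCL.1 (Section 5.10.3.2) says that "analyses for endpoints during other time points will include all data before study drug discontinued on Safety population", and it names the same population for the post-treatment period. Under SAP 5.1 the Safety Population combines Algorithm 1 and Algorithm 2 participants into one LY3209590 group. SAP 5.10 makes that pooled group versus degludec the default safety comparison. SAP 5.1 also defines an Efficacy Population limited to Algorithm 1 and degludec, but Table BDCL.1 does not use it. The revision history in SAP 3 says this version was brought into line with amendment (d).

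**The concern.** The two documents assign different populations to a stated secondary endpoint, the incidence and rate of hypoglycemia during treatment. The protocol wording is not a leftover, since it was revised in the same amendment that removed Algorithm 2.

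The choice matters because hypoglycemia depends directly on how the dose is set, and Algorithm 2 was stopped over problems with its dose recommendations. Primary HbA1c compares Algorithm 1 with degludec. With hypoglycemia reported only for the pooled arm, glycemic benefit and hypoglycemia risk cannot be read on the same participants for that comparison.

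Pooling also raises a comparability question. The protocol's amendment history records that Algorithm 2 randomization was withdrawn in the EU, so the share of pooled LY3209590 participants can differ by country. The rate comparison in SAP Appendix 1 is unadjusted, and the incidence model adjusts only for baseline HbA1c.

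**Working it through.** **1. Populations side by side**

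| Analysis | Protocol 9.4.6.3 | SAP Table BDCL.1 |
|---|---|---|
| Level 1, Level 2 | Efficacy Population (no Algorithm 2) | Level 1 and Level 2/3 on the Safety Population (Algorithm 2 pooled) |
| Level 3 | Efficacy and Safety Populations | Within Level 2/3, on the Safety Population |
| Any analysis without Algorithm 2 | Yes | None |

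**2. Is the change recorded or explained?** The SAP 3 revision history has three relevant entries.
- Alignment with amendment (d), which the footnote contradicts.
- A change of method for hypoglycemia rates, from negative binomial regression to the empirical method, which does not concern the population.
- A general entry on added detail that gives analysis population as an example, without naming hypoglycemia or offering a reason.

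The optional sensitivity analysis in SAP 5.1 removes participants who departed markedly from the dose algorithm. It does not remove the Algorithm 2 arm.

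**3. Scope.** Table BDCL.1 has 2 levels (Level 1, Level 2/3), 3 types (documented, nocturnal, non-nocturnal) and 4 periods (0-12, 0-26 and 12-26 weeks, and post-treatment).
- Rates: 2 × 3 × 4 = 24. Incidences: 2 × 3 × 4 = 24. Total: 48.
- On treatment: 2 × 3 × 3 × 2 = 36. Post-treatment: 2 × 3 × 1 × 2 = 12.
- On the Efficacy Population: 0.

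The 48 is an upper bound, because the incidence model is fitted only when at least 10 patients have the event. The two composites of HbA1c target without nocturnal hypoglycemia are not counted.

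**4. What flash glucose monitoring (FGM) covers.** SAP 5.1 and 5.11.1 keep FGM hypoglycemia on Algorithm 1 versus degludec. The two on-treatment sessions last at most 2 × 14 = 28 days, out of 26 × 7 = 182 treatment days: 28/182 = 15.4%. The first ends at Visit 15 (Week 12), so it starts no earlier than about Week 10.

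**5. Possible effect of pooling (illustration only).** The documents give no Algorithm 2 count and no event rate. Assume 125 Algorithm 1 participants (the planned number in protocol 9.2), m Algorithm 2 participants, equal exposure per participant, and an Algorithm 2 event rate k times the Algorithm 1 rate. Pooling then multiplies the LY3209590 rate, and the rate ratio to degludec, by (125 + mk)/(125 + m).

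| m | Share of pooled arm | k = 0.5 | k = 2 |
|---|---|---|---|
| 5 | 3.8% | 0.98 | 1.04 |
| 10 | 7.4% | 0.96 | 1.07 |
| 20 | 13.8% | 0.93 | 1.14 |
| 40 | 24.2% | 0.88 | 1.24 |
| 60 | 32.4% | 0.84 | 1.32 |

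Both m and k are assumed. The amendment (d) rationale mentions only a "limited number of Algorithm 2 dosing recommendations observed from a limited number of sites and participants during the early enrollment phase".

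**6. Primary analysis.** The one design figure in the plan, power above 80% with 100 completers per arm, does not depend on this point. It reproduces: SE = 1.1 × √(2/100) = 0.1556, 0.4/0.1556 = 2.571, and 2.571 − 1.645 = 0.926, which gives 82.3%.

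**The case against.** **The protocol leaves hypoglycemia details to the SAP.** Section 9.4.1 does so, and the footnote's split at drug discontinuation is a fair example of such a detail. The 9.4.1 exemption is also weaker evidence than 9.4.6.3, because the rule it modifies covers a data window as well as a population. But 9.4.6.3 fixes the population, and replacing it is a change.

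**The clinical study report could still give the reason.** SAP 5.1 allows the SAP and/or the report, whereas protocol 9.4 requires both. A later explanation is possible, but it would not prespecify the missing analysis.

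**An unpooled diary result may exist elsewhere.** The composites' own period cell carries no asterisk, and the Level 1 subgroup rates in SAP 5.12 name no population. However, the asterisk is also on the time-point column header, so the footnote naturally covers the composites. The subgroup rates fall under the pooled safety default unless otherwise specified. Neither gives a stated Algorithm 1 result.

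**FGM is richer than 15.4% suggests.** At 96 readings per 24 hours, 28 days yield up to 2,688 readings per participant. This stands: unpooled hypoglycemia data are not absent. They miss early titration and are not the diary-reported endpoint.

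**A count of 48 is not an effect size.** Correct. One footnote generates all of them, the periods overlap, and half are Level 2/3 composites containing Level 3 events, which the protocol also allows on the Safety Population. The count shows scope only.

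**The two Efficacy Population definitions differ.** The SAP requires at least one dose and the protocol does not. This is immaterial to on-treatment events.

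**The pooled result answers the objective.** The secondary safety objective names LY3209590, not Algorithm 1, and a pooled HbA1c analysis is planned to go with it. This stands, and is a reason to keep the pooled table.

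**Conclusion.** The concern holds. The SAP replaces the population that protocol 9.4.6.3 specifies for Level 1 and Level 2 hypoglycemia, gives no reason, and plans no Efficacy Population version. Level 3 is in conflict only because its Efficacy Population analysis is missing.

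The effect on results cannot be sized. It could be negligible if few participants received Algorithm 2, or material if they were many and their event rate differed. Nothing in the documents indicates its direction. The conclusion rests on the text of the two documents, not on the illustrative factors. The flaw affects a secondary endpoint and leaves HbA1c non-inferiority untouched, so it should be corrected but does not threaten the trial's main conclusion.

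**What to change.** In SAP 5.10.3.2 and the Table BDCL.1 footnote:
- Make the Efficacy Population (Algorithm 1 versus degludec) the main analysis for Level 1 and Level 2/3 rate and incidence.
- Report Level 3 on both populations.
- Keep the pooled Safety Population table as a sensitivity analysis.

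If the sponsor wants the Safety Population as the main analysis, the SAP should justify the departure from protocol 9.4.6.3 and still report the Efficacy Population result. Protocol 9.4 strictly requires only the justification. The added result is recommended because it alone pairs hypoglycemia with the primary HbA1c comparison.

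The SAP should also state the population for the two HbA1c-target composites. The footnote appears to put them on the Safety Population, while the related HbA1c-target analyses in SAP 5.8 follow the Efficacy Population default. The protocol does not name these composites, so the choice is the sponsor's.

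The cost is SAP wording and one extra set of tables on a population already defined in SAP 5.1. The main table loses the Algorithm 2 participants, whose number is not given, but they remain in the pooled table.
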